### **Ask them the date for the next session and record in coversheet**

- If you're able to complete your first set of surveys today [before next session], then I'll go ahead and send you that link to the quick survey for you to do.
- Now, the next three times we'll ask for you to complete surveys will be at Weeks 4, 8, and 12 during your participation. These will take between 45-60 minutes to complete and will involve a 10-15 minute phone call with a member of our research team and then an online survey that will take about 30 minutes answering questions about your mood, your satisfaction with the treatment you are receiving, and questions about your experience with your therapy and therapist.

## WILLOW Full RCT Patient Protocol

The information you provide during this study will be used for research purposes only; it will not be shared with your therapist or treatment team. Your treatment and your participation in our study are separate but parallel activities. You are doing them at the same time but there will not necessarily be any cross over between the two EXCEPT for during the research appointments I just described to you where we'll ask about how sessions are going and what type of activities you do in session, etc. Everything you do for the research will be either on the phone or on SurveyMonkey, where the surveys are located. Everything else <>for WILLOW patient participants specify measures, videos, worksheets, etc in WILLOW>> would be for your therapy separate from the research. If you ever need clarification, please ask your provider or contact us.

As you know, the length of research-based treatment is 12 weeks. After the 12-week period, you and your therapist or clinic will decide what your next steps for treatment will be. If you have questions about this, we encourage you to talk with your therapist or clinic before enrolling in the study. While the research trial is 12 weeks, this does not mean you must quit treatment after 12 weeks or that you are obligated to continue treatment for 12 weeks. If more treatment is needed after the 12-week period, you will work with your therapist and the clinic to decide how to proceed. If you decide to stop treatment before the 12 weeks of your study participation are over, we ask that you still complete the online surveys and phone calls, regardless of whether or not you are still receiving treatment from your study therapist.

As compensation for your study participation and time involved in completing the online surveys and phone calls, you will receive \$40 for each of your Week 4 and Week 8 surveys, and \$60 for your Week 12 survey, for a total of \$140 if you complete all study procedures. The payment will be coming from Chase Bank so be sure to keep an eye out for envelopes from Chase when the time comes.

Since completing your surveys in a timely manner is really important to the research, each survey and phone call you complete within one week of the scheduled appointment date will qualify you to earn a chance to win a tablet in a raffle drawing that will happen at the end of the study. For example, if you complete all four sets of surveys on time, you will earn four chances to win the tablet in the raffle drawing.

Do you have any questions about the study so far?

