## WILLOW Full RCT Patient Protocol

**If yes, continue with the script**

**If no, thank them for considering the study and end call**

**Describe next steps:**

Okay, I'd like to summarize the next steps for us now. I will send you the link to our online consent form for you to complete after this call.

- It will review the information we just discussed and also provide you with more details about participating in this study.
- The survey will also include more information about The Health Insurance Portability and Accountability Act (HIPAA)

After you're done with the consent form, the survey will direct you back to the email I'll be sending to you in a minute. There will be another link in the email that will take you to the first set of surveys. We expect that they will take about 30-45 minutes to complete. This survey will ask for your study ID, if you have something to write on I can provide that right now? Or I can text it to you if that's better for you. Which do you prefer?

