**Make sure to text or read aloud the study ID to the patient.**

If you have any questions or if you experience any difficulty with the survey system, please call or email us immediately. We're here to help! Once you have completed the surveys, please call or text or email me back at my direct line you'll find in the email I will send you to record the completion of that survey. I will also ask for the date of your next therapy session. After this, we will let your therapist and/or clinic know you are ready to schedule your first study session. After your first visit with your therapist, we will call you to schedule your next three study assessments and also send you the link to one final survey to complete as part of your first bundle of survey measures.

Do you have any final questions for me? Excellent! I will now email you the link to the consent form and your first set of surveys. Thank you for talking with me today. If you have any questions or concerns as you are reviewing the consent form or completing the surveys, please don't hesitate to contact me and remember to give me a call when you're finished with the surveys. Thank you!

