**Action items while participant completes baseline surveys:**

1. Check the debrief items at the end of the survey
2. If participant reports a score of 5 or greater on items 3a, 3b, or 4b **call them** and do [mood induction protocol](#) (see [flowchart](#) for the coping skills)
3. If they do not answer leave a voicemail (script below)

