## WILLOW Full RCT Patient Protocol

there are things that you have found helpful to do in situations like this or if you and your therapist have identified something that is helpful for you to try, we will ask that you do these now. We can also suggest other activities to try that may help improve your mood. Our study procedures also require that we contact your therapist unless we hear back from you in the next few minutes. Thank you again for completing this assessment. I look forward to hearing back from you.

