### 5. If participant does not respond soon, call and email their provider

#### **When participant calls you back after completing consent and baseline:**

1. Thank participant for completing the Consent process and baseline surveys; let participant know you will be sending them a copy of their Consent Form and HIPAA authorization via email shortly.
2. Proceed through debrief protocol if needed
3. Collect date of next therapy session and schedule assessments if they know.

~~~~~

Step 4: Action Steps after Informed Consent Call

1. Send the patient a link to the consent form/HIPAA authorization/baseline surveys in an email.
 - a. Study IDs = first three digits of therapist Study ID and fourth digit the number of patient assigned to the therapist.
Example: This patient is the third study patient the therapist is treating. The therapist ID is 117. → Patient ID = 1173
 - b. If patient hasn't yet been assigned to a therapist, they will be numbered in consecutive order, starting with 3001
2. Log that the phone call has been completed in the cover sheet and that the consent form and baseline are pending
3. Log that the phone call has been completed and the consent and baseline have been sent in the [Participant Tracking DB](#)

WILLOW Full RCT Patient Protocol

4. Check back in two hours if you haven't heard back from patient to see if they filled out the consent form and baseline assessment on survey monkey.
 - a. If they have not completed the consent form or baseline, call and email the participant to check in; reschedule as needed.
5. When they complete the consent form, check to make sure all answers are filled in the consent form and that they agree to participate in the study. Make note if they answer No to any of the authorization questions and discuss at next Research Meeting
6. Log the consent completion into the database and cover sheet
7. Log the Baseline completion into the database and cover sheet

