- Discuss raffle (how many raffle tickets they earned) and that we will let the winners know by email and phone. Drawing will take place once all participants have completed the study.
- Put cover sheet into the [Completed Folder](#).

Transition from Assessment to Mood Induction

STEP 1: Orient to Mood Induction [if patient reports a score of 5+ on items 3a, 3b, 4b]. You mentioned on that mood rating that you are feeling <<insert what person endorsed, e.g., "like using drugs" or "like killing yourself" or "like harming someone else">>. I just want to make sure that you're in good shape before we hang up. Would it be okay with you if we take a few moments to see if we can get your mood up a bit before we hang up?

If really distressed, use/discuss Acute Skills, slides 3-7

STEP 2: Distress Due to Assessment? Is how you're feeling now like how you often feel, or does it feel worse than typical, maybe because of going through the study processes?

Survey Monkey Link to Debrief Protocol: <https://www.surveymonkey.com/r/3LV2HS8>

STEP 8: Managing an Acute Crisis:

For use when participant is extremely upset and/or you are uncertain about how to proceed.

Validate Person's Plan & Desire to Help.

I can tell you are still having a hard time. I want to make sure that you are okay and safe after we hang up.

<<Go to STEP 5 (slide 1), "Teach Additional Coping Skills">>

If you haven't yet taught TIPP, introduce and teach now or practice a different TIPP skill if you have already covered some skills previously.

Acute Skills (really distressed)

- Cold water/Ice pack on face
- Paced Breathing and other

TIPP Skills (slide 2).

[name]: [contact]

Emergency / Crisis Situation.

If participant seems unresponsive or not willing to seek help, call
[name] [contact] or **[name] [contact]**.

State to participant: *I am very worried about you and I'd like to get help from my supervisor who is a clinical psychologist if you don't mind. May I briefly put you on hold while I attempt to reach her? If I can reach her, I'll tell her a bit about what we discussed and I'll have her join the line with us. Is that okay with you?*

Inform Clinic of Event.

Discuss event with [name] or [name] so they can contact clinic emergency contact to inform them of the event. The clinic contact will decide how next to proceed with client and therapist as determined by clinic-specific protocols.

TIPP Skills:

T

TEMPERATURE CHANGE:

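### The spoken consent-call script tells patients without qualification that study information stays from the therapist, while the risk procedure requires provider contact when a flagged patient is not reached

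*Protocol*

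**What the plan says.** **The spoken statement.** In the Patient Protocol, Step 3 (Patient Informed Consent Call), the research assistant says of the information the patient provides that "it will not be shared with your therapist or treatment team". A little later the script separates research from treatment, "EXCEPT for during the research appointments I just described to you". Near the end it mentions one contact with the therapist: after the baseline surveys, "we will let your therapist and/or clinic know you are ready to schedule your first study session". It also says that an online consent form will follow, which will "provide you with more details about participating in this study".

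**The risk procedure.** Staff check the mood items at the end of each survey. The trigger is a score of 5 or more on item 3a (urge to self-harm), 3b (intent to kill oneself) or 4b (intent to hurt another person). Staff then telephone the patient. If nobody answers, they leave a voicemail and send an email, both of which state: "Our study procedures also require that we contact your therapist unless we hear back from you in the next few minutes". The staff instruction is "If participant does not respond soon, call and email their provider". The crisis page (Transition from Assessment to Mood Induction, Inform Clinic of Event) adds that senior staff should be told so that they can "contact clinic emergency contact to inform them of the event".

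**A loose end.** Step 6 of the Mood Assessment and Debrief Protocol sends a patient who wants to end the call early to Step xx. The steps are numbered 1 to 8.

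**The concern.** The sentence describes who will see what the patient tells the study, and it has no limit. The risk procedure sets a limit, and the study's own voicemail and email call the resulting contact required. A patient who relies on the spoken assurance and then reports suicidal or violent intent could find the therapist contacted within a short time, having been told on the telephone that information would not go there.

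What is at stake is the accuracy of a statement made to participants about a sensitive matter. The safety contact itself is appropriate; only the way it is described in advance needs correcting. The Step xx gap matters less: it leaves a research assistant to work out what to do when a flagged patient wants to hang up before a coping plan exists.

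**Working it through.** No arithmetic tests this point, and the plan states no figure to reproduce. The check is to set the texts side by side.

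1. **Does the call script qualify the assurance?** I read the whole of Step 3, from the greeting to the closing. Two places could serve as a qualifier.
   - The clause quoted from the same paragraph is about researchers asking the patient how therapy is going. It concerns information flowing from therapy into research, not from research to the therapist.
   - The later mention of the therapist is about readiness to schedule a session. It is not a safety notice.
   - Safety exceptions found in the call script: 0.

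2. **Does the risk procedure require provider contact?** The instruction to call and email the provider of a flagged patient who is not reached appears in three places: after the baseline surveys (Step 3), after the Week 4, 8 and 12 surveys (Step 9), and in the Mood Assessment and Debrief Protocol. The trigger is the same each time. The crisis page adds a route to the clinic that does not depend on the patient being unreachable.

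3. **Does recorded permission resolve the conflict?** Step 2 has staff note whether the patient allows contact with the therapist or clinic. Step 4, item 8 uses permission to decide whether staff may discuss study participation, with a workaround when it is refused. None of the three risk instructions, nor the crisis page, depends on that permission. For a patient who refused it, the gap between the spoken assurance and the procedure is widest.

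4. **When does a patient first hear of required contact?** The scripted order is: the spoken assurance; payment, raffle, voluntariness and next steps; the online consent form with HIPAA information; the baseline surveys; and the mood items at the end of them. In the supplied scripts, the first statement that the study must contact the therapist is the voicemail or email sent after a flagged answer. The automatic on-screen message suggests that the patient call the therapist but does not say that staff may. The written consent step lies between the call and the mood items, and its content cannot be seen.

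5. **How often can it arise?** The check runs at 1 baseline + 3 follow-up assessments = 4 per patient. The documents give no expected number of flagged patients, unreached patients or early hang-ups, so no count can be derived. The patient-facing statement of required contact is one voicemail text and one email text, each printed three times (2 × 3 = 6 printings). That repetition shows the procedure is consistent; it does not measure impact.

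6. **Step xx.** Step 7 (concluding the call) follows directly and is the likely target. It opens, however, by summarizing a plan, which a patient leaving during Step 6 may not have made. Step 8 covers a very upset patient or an uncertain assistant. A sensible route exists, but this script does not name it.

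**The case against.** The strongest objection is that the call is only an overview. Formal disclosure belongs in the online consent form and HIPAA authorization, which the patient completes before any mood item and which may well state the safety exception. Those pages are not in the supplied documents, and their absence cannot be counted against the plan. Therapist contact had also been raised earlier, through the permission question at screening.

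Much of this stands. A reader might infer that patients consented without knowing about safety contact, or that the assurance is the last thing they hear before the risk items. The documents support neither, because the written step comes in between and is unseen. A reader might also infer that item answers are passed to the provider. The instructions say to call and email but do not say what is disclosed, so that is likely but not stated.

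What does not stand is the idea that a correct form cures the sentence. If the form states the exception, the patient receives a spoken statement and a written one that disagree. The permission question does not help either, since the risk procedure does not depend on it.

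On Step xx, it is fair to say that Step 7 is the next heading. The flowchart that staff use may also name the route, and it is only partly visible here. This is close to a clerical slip.

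**Conclusion.** The sentence in the consent-call script is wrong as written. It promises that study information will not reach the therapist or treatment team, and the study's own procedure requires provider contact for a flagged patient who is not reached, and notice to the clinic in a crisis. The finding covers the spoken script only and assumes that staff follow it as printed. It says nothing about whether the consent process as a whole was adequate.

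The size is small in text and unknown in patients. A reader might look for a consequence for the trial's results, but the documents give no basis for one: nothing here touches outcomes, power or the analysis. It is a participant-protection correction that should be made because it is cheap and the assurance concerns self-harm and violence. The Step xx edit is minor and secondary.

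**What to change.** **Main edit.** In Step 3, directly after the quoted assurance, add: *There is one exception: if your answers suggest you may harm yourself or someone else and we cannot reach you promptly, or if there is a crisis, we will contact your therapist or clinic, whether or not you gave us permission to discuss your study participation with them.* The verb should be *will*, because the voicemail and email describe the contact as required. Then confirm that the consent form and HIPAA authorization say the same.

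**Secondary edit.** In Step 6 of the debrief script, replace Step xx with: the part of Step 6 on whom the patient can call, if the patient allows it, then the closing part of Step 7 (Conclude the Call); go to Step 8 if the patient is acutely distressed or the assistant is uncertain how to proceed. This avoids the opening of Step 7, which assumes a plan has been made.

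**Cost.** One sentence, one cross-reference, a check of two forms and an ethics-board notification. No new staff, visits or data are needed. Some patients may answer the three items less candidly once they know of the exception; the documents give nothing to size this. The SAP, dated February 8, 2020, reports the analysis in the past tense, so the script edits would serve later use of these materials rather than patients already assessed. The check of the two forms can still be done now.

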**If there are no questions, move on to the next section**

Participation in this study is completely voluntary. You can decline at any time if you are not interested in participating.

Now that you know a more about the study, are you still interested in participating? Do you have any questions?

## WILLOW Full RCT Patient Protocol

**If yes, continue with the script**

**If no, thank them for considering the study and end call**

**Describe next steps:**

Okay, I'd like to summarize the next steps for us now. I will send you the link to our online consent form for you to complete after this call.

- It will review the information we just discussed and also provide you with more details about participating in this study.
- The survey will also include more information about The Health Insurance Portability and Accountability Act (HIPAA)

After you're done with the consent form, the survey will direct you back to the email I'll be sending to you in a minute. There will be another link in the email that will take you to the first set of surveys. We expect that they will take about 30-45 minutes to complete. This survey will ask for your study ID, if you have something to write on I can provide that right now? Or I can text it to you if that's better for you. Which do you prefer?

**Make sure to text or read aloud the study ID to the patient.**

If you have any questions or if you experience any difficulty with the survey system, please call or email us immediately. We're here to help! Once you have completed the surveys, please call or text or email me back at my direct line you'll find in the email I will send you to record the completion of that survey. I will also ask for the date of your next therapy session. After this, we will let your therapist and/or clinic know you are ready to schedule your first study session. After your first visit with your therapist, we will call you to schedule your next three study assessments and also send you the link to one final survey to complete as part of your first bundle of survey measures.

Do you have any final questions for me? Excellent! I will now email you the link to the consent form and your first set of surveys. Thank you for talking with me today. If you have any questions or concerns as you are reviewing the consent form or completing the surveys, please don't hesitate to contact me and remember to give me a call when you're finished with the surveys. Thank you!

**Action items while participant completes baseline surveys:**

1. Check the debrief items at the end of the survey
2. If participant reports a score of 5 or greater on items 3a, 3b, or 4b **call them** and do [mood induction protocol](#) (see [flowchart](#) for the coping skills)
3. If they do not answer leave a voicemail (script below)

**Voicemail Text (if patient does not answer when research team calls):**

Hi \_\_\_\_\_, this is \_\_\_\_\_ from Evidence-Based Practice Institute. Thank you for completing the research study surveys. I see that you reported you are feeling like harming yourself or someone else. It's not uncommon for people who are completing an assessment like this one to notice a drop in their mood. Please contact me right away by calling xxx-xxx-xxxx. If

## WILLOW Full RCT Patient Protocol

there are things that you have found helpful to do in situations like this or if you and your therapist have identified something that is helpful for you to try, we will ask that you do these now. We can also suggest other activities to try that may help improve your mood. Our study procedures also require that we contact your therapist unless we hear back from you in the next few minutes. Thank you again for completing this assessment. I look forward to hearing back from you.

### 4. Follow up with email text

Dear XXX,

Thank you for completing the research study surveys today. I would like to talk with you about some of your answers on the last survey. Please contact me right away by calling xxx-xxx-xxxx. Our study procedures also require that we contact your therapist unless we hear back from you in the next few minutes.

Thank you again for completing these surveys today. I look forward to hearing back from you.

Kind Regards,

Xxx

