Think of the positive consequences of tolerating the distress. Imagine in your mind how good you will feel if you achieve your goals, if you don't act impulsively.

Think of all of the negative consequences of not tolerating your current distress. Remember what has happened in the past when you have acted impulsively to escape the moment.

Ask yourself, "*Will this event that is distressing me going to matter in 5 years?*"

WILLOW RCT
Mood Assessment and Debrief Protocol

**Adapted from Linehan's
Suicide Risk/Distress Assessment Protocol**

PURPOSE:

While the risk is deemed low, the intent of this Mood Induction Protocol is to ensure that research patients are not at imminent risk to harm or kill self following completion of a study assessment.

PROCEDURE:

Before concluding each assessment, the patient will complete the Mood Assessment online. If the patient reports a score of 5 or greater on items 3a, 3b, 4b, they will receive a message from the survey system. This message will include validation of their experience and suggestions for improving their mood through the use of behavioral skills. Specific changes are detailed below.

MOOD ASSESSMENT:

1. Feedback on their experience during this assessment and other experiences they have had with the study (i.e., other assessments -- how did this one compare? How was it different? What made the difference?). Describe.

2. ____ On a scale of 0 to 7, what is your level of stress right now?

Low 0 1 2 3 4 5 6 7 High

- 3a. ____ On a scale of 1 to 7, what is your urge to harm yourself now?

Low 0 1 2 3 4 5 6 7 High

- 3b. ____ On a scale of 1 to 7, what is your intent to kill yourself right now?

Low 0 1 2 3 4 5 6 7 High

4. ____ On a scale of 1 to 7, what is your urge to use drugs or alcohol right now?

Low 0 1 2 3 4 5 6 7 High

- 4a. ____ On a scale of 1 to 7, how angry are you (i.e., what is your level of anger right now)?

Low 0 1 2 3 4 5 6 7 High

- 4b. ____ On a scale of 1 to 7, what is your intent to physically hurt another person right now?

Low 0 1 2 3 4 5 6 7 High

If the patient endorses a score of 5 or greater on items 3a, 3b, 4b, they receive the following message:

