You reported that you are feeling like harming yourself or someone else. It's not uncommon for people who are completing an assessment like this one to notice a drop in their mood. Please contact us right away by calling [name] (XXX-XXX-XXXX) or [name] (XXX-XXX-XXXX). If there are things that you have found helpful to do in situations like this or if you and your therapist have identified something that is helpful for you to try, we will ask that you do these now. We can also suggest other activities to try that may help improve your mood. You may also consider calling your therapist, your clinic where you receive services, or call the National Suicide Prevention Lifeline at [name] or go to <http://www.suicidepreventionlifeline.org/> for other helpful information. If this is a clinical emergency, please call 911 right away.

Transition from Assessment to Mood Induction

For use when participant scores 5+ on items 3a, 3b, and/or 4b.

If the patient endorses a score of 5 or greater on items 3a, 3b, 4b, Research Assistant will call and email participant to go through the protocol below (see Steps 1-8). If the Research Assistant is unable to reach the participant, they will call and email the patient's provider.

Voicemail Text (if patient does not answer when research team calls):

Hi _____, this is _____ from Evidence-Based Practice Institute. Thank you for completing the research study surveys. I see that you reported you are feeling like harming yourself or someone else. It's not uncommon for people who are completing an assessment like this one to notice a drop in their mood. Please contact me right away by calling xxx-xxx-xxxx. If there are things that you have found helpful to do in situations like this or if you and your therapist have identified something that is helpful for you to try, we will ask that you do these now. We can also suggest other activities to try that may help improve your mood. Our study procedures also require that we contact your therapist unless we hear back from you in the next few minutes. Thank you again for completing this assessment. I look forward to hearing back from you.

Email Text:

Dear _____,

Thank you for completing the research study surveys today. I would like to talk with you about some of your answers on the last survey. Please contact me right away by calling xxx-xxx-xxxx. Our study procedures also require that we contact your therapist unless we hear back from you in the next few minutes.

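### The voicemail and email for a patient who scores 5+ and does not answer leave out the on-screen 911 advice, and the email also leaves out the therapist, clinic and Lifeline advice

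*Protocol*

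**What the plan says.** The Mood Assessment and Debrief Protocol, under Procedure, sets the trigger and the first response: "If the patient reports a score of 5 or greater on items 3a, 3b, 4b, they will receive a message from the survey system". That on-screen message gives two study contacts and asks the patient to use coping steps they already know. It then adds "You may also consider calling your therapist, your clinic where you receive services, or call the National Suicide Prevention Lifeline at" (the number is removed in the public copy, and a website follows) and ends with "If this is a clinical emergency, please call 911 right away".

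The same score has a research assistant call the patient. If the call is not answered, staff leave a scripted voicemail and send a scripted email. The pair is printed three times: in the Patient Protocol at Step 3 (actions while the patient completes the baseline surveys), at Step 9 (actions while the patient completes the week 4, 8 or 12 surveys), and in the Debrief Protocol under Transition from Assessment to Mood Induction. Every copy contains "Please contact me right away by calling xxx-xxx-xxxx" and "Our study procedures also require that we contact your therapist unless we hear back from you in the next few minutes".

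The next step is contact with the provider. Steps 3 and 9 say "If participant does not respond soon, call and email their provider". The Debrief Protocol says "If the Research Assistant is unable to reach the participant, they will call and email the patient's provider".

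**The concern.** These two scripts are used when staff have failed to reach someone who has just reported a strong urge to self-harm, intent to die, or intent to hurt another person. The study judged 911 and crisis-line wording suitable for exactly this score, and put it on the survey screen. Once direct contact fails, the messages that follow offer one route only, a call back to the study. If that line is not answered, or the patient does not want to speak to the study, neither message points elsewhere. What is at stake is participant safety in what is probably a small number of events. No estimate, test or endpoint depends on it.

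**Working it through.** No arithmetic beyond counting applies, so the texts are set side by side.

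| Element | On-screen message | Voicemail (3 copies) | Email (3 copies) |
|---|---|---|---|
| Study callback number | yes (two contacts) | 3 of 3 | 3 of 3 |
| Use known coping steps | yes | 3 of 3 | 0 of 3 |
| Notice that staff will contact the therapist | no | 3 of 3 | 3 of 3 |
| Advice to call therapist, clinic or Lifeline | yes | 0 of 3 | 0 of 3 |
| Advice to call 911 in an emergency | yes | 0 of 3 | 0 of 3 |

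1. *Copies.* 3 voicemails + 3 emails = 6. The 911 line is in 0 of 6. The copies agree with one another, so this is two scripts each printed three times, not six separate lapses.
2. *Redaction.* Removed names and placeholder numbers do not explain the gap, because the whole sentences are absent.
3. *Mentions of the therapist.* Both scripts name the therapist as someone staff will contact. The voicemail also names the therapist as a possible source of coping steps already agreed. Neither advises the patient to call the therapist.
4. *Other routes to the same advice.* A crisis hotline is otherwise offered only in Step 6 of the live debrief call, after the patient's own network and then the therapist have been suggested. That call has not happened for this patient. 911 appears nowhere else in the documents. Step 8, for acute crises, relies on bringing in a supervisor during a live call.
5. *Occasions.* The scripts apply at 4 survey points: baseline and weeks 4, 8 and 12.
6. *Frequency.* How often a 5+ score is followed by an unanswered call is not given. The Debrief Protocol describes the risk as low.
7. *Why the voicemail is judged on 911 only.* It also lacks the therapist/clinic/Lifeline sentence. Because staff both call and email for the same event, an email carrying that sentence would deliver it, and the voicemail can stay short.

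**The case against.** The strongest reply is that the advice has already been given. The score that triggers the voicemail and email also triggers the on-screen message, and nothing in the protocol promises that later scripts will repeat it. Contact should also follow closely: staff check the debrief items while surveys are being completed, and patients are told to get in touch when they finish. If they do not respond, the provider is called and emailed. All of this stands, and it limits the point to a missing repeat.

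A sharper form of the reply is that if the email is enough to carry the Lifeline for the voicemail, the screen should be enough for both. This has some force. But the screen message comes before the failed contact and the email comes after it. The email can be kept and reread, while the documents do not say whether the survey message can be reopened.

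The provider contact is only a partial answer. It depends on non-response, and how long staff should wait is not defined beyond the word soon. At baseline some patients may not yet have a study therapist: Step 3 has a script for that case and Step 4 a separate ID series. No permission condition is printed at this step, so the safeguard should not be discounted on that ground. It is, however, something staff do, and gives the patient nothing to act on meanwhile.

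Privacy is a fair objection to the email change. The email now refers only to some survey answers, and naming the Lifeline shows what it is about. The voicemail already names the report. Whether it should do so is a privacy-versus-urgency choice for the clinical lead, and the documents give no ground for calling it an error.

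A reader might infer that an unreachable high-risk patient is left with no safety net. The documents do not support that, given the on-screen message and the provider contact. A reader might also infer that the voicemail must carry the Lifeline sentence. With the paired email corrected, it need not.

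**Conclusion.** The point holds as a small gap in the safety scripts. The 911 line is missing from 6 of 6 follow-up messages, and the therapist/clinic/Lifeline sentence from 3 of 3 emails. It is worth considering and no more than that. The conclusion assumes that the survey system shows its message as described, and that staff send the email whenever they leave the voicemail, as the Debrief Protocol directs. The number of patients affected cannot be estimated from the documents. No outcome or analysis changes. The SAP, dated February 8, 2020, reports its analyses in the past tense, so the practical gain is likely to lie in any reuse of these scripts.

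**What to change.** - In all three copies of both scripts, add the existing on-screen sentence "If this is a clinical emergency, please call 911 right away".
- In all three emails, after the callback number, add the existing on-screen sentence that begins "You may also consider calling your therapist, your clinic where you receive services, or call the National Suicide Prevention Lifeline at", with its number and website. Keep the neutral opening.
- Leave the rest of the voicemail as it is, including the validation and coping sentences.

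Cost: 3 emails × 2 sentences + 3 voicemails × 1 sentence = 9 insertions, with nothing deleted. The voicemail is one sentence longer, and the email reveals slightly more to anyone else who reads it. If the clinical lead objects to the Lifeline sentence on privacy grounds, the 911 sentence alone can go into both scripts, which is 6 insertions.
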